3.2 Schedule of assessments (SoA)

Table 1. Schedule of assessments for long-term follow-up in COVID-19 patients.

| | COVID-19 (2 weeks ¹ ± 2 weeks) | 3 months ¹ (± 1 month) | 6 months ¹ (± 1 month) | 12 months ¹ (± 2 months) | 18 months ¹ (± 3 months) |
|--|---|--------------------------------------|--------------------------------------|--|--|
| Screening/baseline | | | | | |
| Inclusion criteria ¹ | X | | | | |
| Demographics ² | X | | | | |
| Healthcare setting ³ | X | | | | |
| Length of hospital stay, days | X | | | | |
| ICU admission | X | | | | |
| Medical history ⁴ | X | | | | |
| Treatment | | | | | |
| Comorbidity management ⁵ | X | X | X | X | X |
| Anti-COVID therapy ⁶ | X | | | | |
| Antibiotic therapy | X | X | X | X | X |
| Oxygen therapy ⁷ | X | X* | X* | X* | X* |
| SARS-CoV ² ⁸ and other respiratory pathogen vaccination ⁹ | X | X | X | X | X |
| Clinical assessment | | | | | |
| Relevant medical new events ¹⁰ | X | X | X | X | X |
| COVID-19 symptom ¹¹ onset | X | | | | |
| COVID-19 symptom end | X | X* | X* | X* | X* |
| COVID severity ¹² | X | | | | |
| SOFA score | X | | | | |
| Vital signs ¹³ | X | X | X | X | X |
| Physical examination ¹⁴ | X | X | X | X | X |
| 12-lead electrocardiography | X | X | X | X | X |
| 6-minute walking test | X | X | X | X | X |
| DLCO (diffusing capacity for carbon monoxide) | X | X | X | X | X |
| Pulmonary function test ¹⁵ | X | X | X | X | X |
| Questionnaires | | | | | |
| Functional status ¹⁶ | X | X | X | X | X |
| Respiratory impairment ¹⁷ | X | X | X | X | X |
| Mental health ¹⁸ | X | X | X | X | X |
| Risk perception and behaviour^{19, 20} | | | | | |
| SARS-CoV-2 vaccination: acceptance/non-acceptance and reasons ²¹ | | X | | X | X |
| Socio-economic indicators | | X | | X | X |
| Use of resources (COVID-19 unrelated) | | X | | X | X |
| Imaging | | | | | |
| Lung ultrasound | X | X | X* | X | X* |
| X-ray | X | X | X* | X* | X* |
| High-resolution CT scan | X | X | X* | X* | X* |
| Cardiac ultrasound | X | X | X* | X | X* |
| Cardiac MRI ²² | X ²¹ | X ²¹ | X* | X ²¹ | X* |
| Biochemistry | | | | | |

| | | | | | |
|---|---|-------------------|-------------------|-------------------|----|
| Blood tests ²³ | X | X | X* | X | X* |
| Arterial blood gas test (pO ₂ /pCO ₂ /pH) | X | X | X* | X* | X* |
| Urine tests ²⁴ | X | X | X* | X | X* |
| Immunology | | | | | |
| Immune - serology and type I IFNs autoantibodies | X | X | X | X | X |

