| Immune - cytokine and chemokine | X | X ³⁵ | X ³⁵ | X ³⁵ | X* |
| Immune - cellular | X | X ³⁵ | X ³⁵ | X ³⁵ | X* |
| Microbiological tests-NP swabs | | | | | |
| Viral variant and metagenomics sequencing | X | X*, ³⁴ | X*, ³⁴ | X*, ³⁴ | X* |
| EDTA whole blood | | | | | |
| Genetic and epigenetic analysis | X | X | X | X | X |
| Stool Sample (faeces or rectal swab) | | | | | |
| Metagenomic sequencing | X | | X | | X |
| Microbiological tests | | | | | |
| SARS-CoV-2 molecular test in nasopharyngeal swab or tracheal aspirate or bronchoalveolar lavage or saliva | X | X* | X* | X* | X* |
| Adjunctive variables for specific fragile populations | | | | | |
| HIV | | | | | |
| HIV-infection status ²⁵ | X | X | X | X | X |
| HIV-Infection therapy ²⁶ | X | X | X | X | X |
| Assessment of adherence to follow-up visits and antiretroviral therapy | X | X | X | X | X |
| Elderly | | | | | |
| Cognitive status ²⁷ | X | X | X | X | X |
| Pregnant women/new born | | | | | |
| History of positive SARS-CoV-2 molecular test on amniotic fluid or breast milk ²⁸ | X | | | | |
| History of detection of microthrombotic disease on placenta tissue or umbelical cord tissue | X | | | | |
| Children | | | | | |
| History of positive SARS-CoV-2 molecular test on amniotic fluid or breast milk ²⁹ | X | | | | |
| Biometric paramethers ³⁰ | X | X | X | X | X |
| Transplant | | | | | |
| Transplant general information ³¹ | X | | | | |
| Graft function ³² | X | X | X | X | X |
| Immunosuppressive regimen ³³ | X | X | X | X | X |

| Onco-haematology | | | | | |
|---|---|---|---|---|---|
| Assessment of adherence to oncologic follow-up visits and therapy | X | X | X | X | X |
| Assessment of progression of the disease and relapse | X | X | X | X | X |
| Assessment of adverse events ³⁴ | X | X | X | X | X |

Footnotes

Modular data capture according to level of commitment (level I, level II, level III).

| | |
|-----------------|--|
| Level I | Assessments in level I are mandatory |
| Level II | Customized according to the feasibility of each cohort |

* Reassessed only if outside the normal ranges at the previous assessment or if clinically indicated

1. Day 0: first positive SARS-CoV-2 test

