9.11. Translational Health Science and Technology Institute (THSTI) – India

THSTI will participate in the recruitment of a large cohort of COVID-19 and non-COVID-19 pregnant women participating in the GARBH-Ini (interdisciplinary Group for Advanced Research on Birth outcomes - DBT India Initiative) program. GARBH-Ini Cohort was initiated in May 2015 at the Civil hospital in Gurugram (GCH), Haryana, India. Women are enrolled within 20 weeks of gestation and are followed until delivery and once at postpartum. The enrolled women are followed up at 4-5 time-points across 3 trimesters of pregnancy to document extensive clinical & epidemiological information, varied maternal and neonatal biospecimens and for serial ultrasonographic examination. Accounting for a cohort design to detect epidemiological risk factors & nested case-control design for identifying biomarkers, an a priori sample size of 8000 was estimated. More than 8534 pregnant mothers have been

enrolled till February 10, 2020 since May 2015 with documentation of 7260 pregnancy outcomes.

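### Table 1 asks the two pregnancy-specific items once, 0–4 weeks after the first positive test, so placenta, cord and breast-milk findings are never captured for women followed prospectively from an infection well before delivery

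*Protocol*

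**What the plan says.** Table 1 in Protocol section 3.2 has a block of additional variables for specific fragile populations. The part for pregnant women and newborns has two rows: "History of positive SARS-CoV-2 molecular test on amniotic fluid or breast milk" and "History of detection of microthrombotic disease on placenta tissue or umbelical cord tissue". In both, an X stands in the first visit column and the 3, 6, 12 and 18-month cells are blank. Neither row carries the starred X that the table uses elsewhere for conditional reassessment.

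The first column is headed "COVID-19 (2 weeks ¹ ± 2 weeks" (bracket closed in the table). Its clock is set by note 1: "Day 0: first positive SARS-CoV-2 test". The window is therefore 0 to 4 weeks after the positive test, and Table 1 has no time point anchored to delivery.

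Other population-specific rows are repeated at every visit, for example "Biometric paramethers ³⁰ | X | X | X | X | X", and likewise HIV status, cognitive status and graft function.

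Section 9.11 describes a cohort in which infection can precede delivery by months: "Women are enrolled within 20 weeks of gestation and are followed until delivery and once at postpartum".

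**The concern.** Placental and cord tissue can be examined only once the woman has delivered, and breast milk is in general not available before then. If the positive test comes in mid-pregnancy, the single scheduled entry falls before any of these findings can exist, and nothing in the table brings the question back.

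Two consequences follow. Findings made at delivery have no scheduled place in the record. And because the rows ask about history, a site might enter no for an undelivered woman, which would mix true negatives with women in whom nothing could have been examined. The maternal variables listed in the notes to Table 1, section 12 and section 14.5 include neither delivery date nor gestational age at infection, so an analyst working from those lists could not separate the two groups afterwards. An analysis plan cannot recover data that were never scheduled for collection.

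**Working it through.** **Step 1. Can another part of the protocol supply the data?**

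- The row for relevant new medical events is asked at every visit. Its note gives thrombosis, embolism, infections and malignancies as examples, and no placental, cord, amniotic-fluid or milk finding.
- Section 12 lists no pregnancy or delivery endpoint that would capture these findings by another route.
- Section 14.4 allows retrospective data collection once a case is complete. It adds no time point for women followed prospectively, and relying on it would make ascertainment differ between retrospective and prospective women.
- Sections 15.1 and 15.2 give the ZIKAlliance substudies by title only. They may schedule delivery data for that cohort, but this cannot be checked here.

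None of these repairs Table 1 for prospectively followed women.

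**Step 2. How many women would have delivered by the only scheduled entry?** The protocol states no figure to reproduce. From Table 1, the visit is at v = 2 weeks (nominal) or v = 4 weeks (latest). The following are assumptions, not protocol figures: delivery at week G = 37 to 40, and infection uniform over gestational weeks a to b.

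Share delivered by the visit = max(0, b − max(a, G − v)) / (b − a)

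| Assumed infection window | Delivered by week 2 | Delivered by week 4 |
|---|---|---|
| Whole pregnancy (0 to G) | 2/40 = 5.0% to 2/37 = 5.4% | 4/40 = 10.0% to 4/37 = 10.8% |
| Week 20 to G | 2/20 = 10.0% to 2/17 = 11.8% | 4/20 = 20.0% to 4/17 = 23.5% |
| Third trimester (28 to G) | 2/12 = 16.7% to 2/9 = 22.2% | 4/12 = 33.3% to 4/9 = 44.4% |
| Weeks 14–27 | 0% | 0% |
| Week 36 to G | 2/4 = 50% to 1/1 = 100% | 100% |

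For weeks 14–27 the result is 0% throughout: even with delivery at week 37 and the visit at week 4, infection would have to fall at week 33 or later.

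**Step 3. When would most women have delivered by that visit?** Suppose a fraction f is diagnosed at delivery itself and the rest uniformly over 40 weeks, with delivered share u. Setting f + (1 − f)u = 0.5 gives f = (0.5 − u)/(1 − u). At week 2 this is (0.5 − 0.05)/0.95 = 47%. At week 4 it is (0.5 − 0.10)/0.90 = 44%.

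**Step 4. What if undelivered women are coded no?** The recorded frequency is then the true frequency times the delivered share: a factor of 0.05–0.11 under uniform infection, 0.17–0.44 for the third trimester. This applies only under that coding, which the protocol does not show.

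**Step 5. Do the existing later visits suffice?** Under uniform infection over pregnancy:

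- Month 3 (week 13): 13/40 = 33% to 13/37 = 35% have delivered.
- Month 6 (week 26): 26/40 = 65% to 26/37 = 70%.
- Month 12 at its earliest (10 months, about week 43): 100%.

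For infection at weeks 14–27, 100% have delivered by month 6, since 14 + 26 = 40.

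**The case against.** The strongest reply is that these are adjunctive history items, not endpoints. Section 12 lists no placental, cord, amniotic-fluid or breast-milk outcome, and no objective names placental disease or vertical transmission. That is correct and limits the weight of the point. No comparison by trimester of infection is planned either, so a distorted trimester comparison should not be charged to the protocol.

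Several stronger readings are tempting, but the documents do not support them:

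- *Most women are undelivered at the entry.* This depends on the timing of infection, which is not given. It holds for infection spread over pregnancy or over the third trimester, and can fail where diagnoses cluster at term. The Bahia cohort (section 9.8.4) recruits women admitted to a maternity hospital, with gestational age not stated.
- *Loss is near total in GARBH-Ini because women enrol by 20 weeks.* Gestation at enrolment is not gestation at infection. These women are followed to delivery and can be infected at any time until then. For infection from week 20 onward, 10–12% have delivered by week 2 and 20–24% by week 4.
- *Only infections shortly before delivery can ever be recorded as positive.* The study is also retrospective (section 8), so a woman entered after delivery can have the items completed whatever her gestation at infection. A newborn index case has a Day 0 after birth, and amniotic fluid can be sampled before delivery.
- *The data will be falsely negative.* No eCRF coding is shown, and section 14.5 provides queries for missing data. The fields may simply be blank.

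What the reply leaves standing is the schedule itself. For a woman followed prospectively from an infection well before delivery, no entry is planned at a time when the answer could exist. A query about a blank field at the first visit does not create one.

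**Conclusion.** The point holds as a gap in the data-collection schedule. The two pregnancy-specific items are asked once, 0–4 weeks after the first positive test, and are not reopened. For prospectively followed women infected more than about 4 weeks before delivery, the placenta, cord and breast-milk items are therefore missing or, depending on coding, entered as no. Women entered after delivery, newborn index cases and amniotic-fluid results available by the first visit are unaffected.

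The size cannot be fixed from the protocol. Across the assumed infection windows, the share already delivered at the entry runs from 0% (weeks 14–27) to 100% (from week 36, at the latest visit date). These figures rest on uniform infection within each window and delivery at 37–40 weeks. No section 12 endpoint is affected. The correction is still worth making, because it determines whether the data exist at all.

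**What to change.** In Table 1, keep the X at the first visit for both rows, because some first-visit entries are valid and moving the rows would lose them. For women undelivered at that visit, add an entry at the first already scheduled visit after delivery (month 3, 6 or 12).

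Record delivery date and gestational age at Day 0. Code *not yet delivered* and *not tested* separately from *negative*. Report frequencies among delivered and tested women.

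While editing, reconcile note 28, which mentions only amniotic fluid although its row also covers breast milk.

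The cost is a few extra eCRF fields and one repeated entry at a visit that already exists. No new test or visit is needed.

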24. Urine tests: pH, concentration, protein, glucose, red blood, white blood cell count
25. CD4 lymphocyte count; HIV-viral load; AIDS status
26. HIV-therapy: drug name and dose (only ongoing treatment); previous switch to other regimens for virological failure
27. Questionnaires to address cognitive status: Cognitive Failure Questionnaire (CFQ), Mini-Mental State Examination, Clinical Dementia rating Scale, Montreal Cognitive Assessment (MOCA).
28. Results of SARS-CoV-2 molecular test on amniotic fluid
29. Weight, height/length, cranial circumference, BMI
30. Type of transplant (heart, lung, kidney, liver, pancreas); single-combined; year of transplantation
31. Graft function: good, impaired, failure, rejection acute-chronic, recurrence of underlying disease, other
32. Immunosuppressive regimen: drug name and dose
33. According to Common Terminology Criteria for Adverse Events (CTCAE)
34. At least one of three timepoints (month 3, month 6, month 12) is required to perform metagenomics analysis.
35. At least one of the three timepoints (month 3, month 6, month 12) is required.

Table 2. Schedule of post-vaccination assessments

| | 1 st dose | 2 nd dose ² | 3 months (± 1 month)* | 6 months (± 2 months)* | 12 months (± 3 months)* |
|--|----------------------|-----------------------------------|--------------------------|---------------------------|----------------------------|
| Baseline information¹ | | | | | |
| Underlying fragile condition | X ¹ | X ¹ | | | |
| Healthcare setting (i.e. LTCF) | X ¹ | X ¹ | | | |
| Comorbidities | X ¹ | X ¹ | | | |
| Concomitant medical treatments | X ¹ | X ¹ | | | |
| Past and/or new COVID-19 disease ³ | X ¹ | X ¹ | X | X | X |
| Clinical evaluation | | | | | |
| Relevant medical new events ⁴ | X | X | X | X | X |
| Clinical symptoms suggestive of COVID-19 | X | X | X | X | X |
| Lab assessment | | | | | |
| Whole blood count | X | X | | | |
| CD4/CD8 count | X | X | | | |
| IgG level | X | X | | | |
| C3 level | X | X | | | |
| Immunology | | | | | |
| Immune - serology and type I IFNs autoantibodies | X | X | X | X | X |
| Immune - cytokine and chemokine | X | X ⁷ | X ⁷ | X ⁷ | X ⁷ |
| Immune - cellular | X | X ⁷ | X ⁷ | X ⁷ | X ⁷ |
| Microbiological tests-NP swabs | | | | | |
| Viral variant and metagenomics sequencing | X ⁵ | X ⁵ | X ⁶ | X ⁶ | X ⁶ |
| EDTA whole blood | | | | | |
| Genetic and epigenetic analysis | X | | X | X | X |
| Stool Sample (faeces or rectal swab) | | | | | |

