11. STUDY PROCEDURES

In Figure 1, a study work flow is shown.

Figure 1: study work flow

All included patients will be evaluated during the scheduled visits for the underlying condition. During such visits, the following actions are required:

- Distribution of a questionnaire to capture the impact of COVID-19 pandemic on the socio-economic indicators, on the access to health care services, and to investigate risk perception and behavior towards preventing infection and COVID-19 disease, including vaccine acceptance. This questionnaire should be administered at two different time-points with an interval of at least 6 months to capture changes in behavior over the study period (Annex 1a or Annex 1b in case of children cohorts).

- Distribution of psychological scale questionnaires to investigate the impact of lockdown measures on mental health (Annex 2).
- Screening for past and/or current COVID-19 disease by medical interview, serology determination and nasopharyngeal swab or saliva specimens' collection.
- Collection, processing and storage of plasma for cytokine and chemokine analysis.
- Collection, processing and storage of serum for the subsequent sero-neutralization and type I IFNs autoantibodies detection.
- Collection, processing and storage of PBMCs for the subsequent anti-COVID-19 cellular immunity analysis.
- Collection, processing and storage of whole blood for genetic and epigenetic analysis.
- Collection, processing and storage of nasopharyngeal samples for SARS-CoV-2 detection and variant identification if clinically relevant.
- Collection, processing and storage of stool samples for metagenomic sequencing.
- In immunocompromised fragile cohorts, laboratory tests to assess the baseline “net state of immunosuppression” including whole blood count, lymphocyte differentiation, immunoglobulin levels, and complement (C3) levels should be done at the baseline (first clinical evaluation).

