The WP6 protocol outlines the objectives of the biological studies foreseen within the project, the methodology to be utilized to meet these goals, which patient populations that are to be analyzed, and how these samples are to be handled and stored.

Target of the document

The target audience of the document are the clinical WPs 2-5 within the ORCHESTRA study in which prospective sample collection is conducted.

Dissemination level

Confidential, only for members of the consortium (including the Commission Services).

Core content

The WP6 prospective protocol document is available in Appendix 1.

References

N/A

Acknowledgments

N/A

Appendix 1

PROSPECTIVE SAMPLE COLLECTION AND MANAGEMENT DOCUMENT

WP6 – Biobanking, genomics, and viral-host interactions

University of Antwerp (UANTWERPEN) in collaboration with all WP6 partners

Version dated 11-05-2021

Thank you for your participation in the ORCHESTRA study. The purpose of this document is to provide you with additional information and instructions on the collection and processing of samples for WP6 within the prospective tier of ORCHESTRA. This document is a guideline for research staff including (sub-) investigators, research nurses, and laboratory staff. The clinical protocol takes precedence over this document. If there is a discrepancy between the sample collection and management document and the clinical protocol, the ORCHESTRA clinical protocol should be followed.

This document outlines how samples should be handled after patient inclusion. Specifically, it describes the time points desired for biosampling.

Project Classification

| | |
|-------------------------|---|
| Project Acronym: | ORCHESTRA |
| Project Title: | Connecting European Cohorts to Increase Common and Effective Response to SARS- CoV-2 Pandemic |
| Coordinator: | UNIVR |
| Grant Agreement Number: | 101016167 |
| Funding Scheme: | Horizon 2020 |
| Start: | 1st December 2020 |
| Duration: | 36 months |
| Website: | www.orchestra-cohort.eu |
| Email: | [contact] |

Document Classification

| | |
|-------------------------------|--|
| Title: | PROSPECTIVE SAMPLE COLLECTION AND MANAGEMENT DOCUMENT |
| Lead Beneficiary: | UANTWERPEN |
| Other Involved Beneficiaries: | INSERM, APHP, UNIBO, HMGU |
| PIs, Participating centres | [name], UANTWERPEN [name], UANTWERPEN [name], UNIBO [name], UNIBO [name], INSERM/APHP [name], INSERM [name], HMGU |

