2.8 RESPIRATORY MICROBIOME DYNAMICS (TASK 6.9)

We will investigate differences in the respiratory microbiome composition by combining meta-transcriptomic and metagenomic sequencing to analyse both RNA and DNA viruses and the bacterial and fungal fractions. This will firstly elucidate the role of commensal flora and of co-infecting respiratory pathogens in influencing COVID-19 disease severity. Secondly, long-term carriage and impact of SARS-CoV-2 on the respiratory microbiome will be assessed on longitudinally collected prospective samples (6-12 months post-recovery and new infections).

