3.1.1 Sample collection and management

Sampling is required to be performed on the day of diagnosis and at following timepoints as shown in Table 2. Patient inclusion will primarily be based on availability of informed consent for the outlined tasks as well as availability of multiple samples per patient. Informed consent forms should clearly request permission to perform human genetic and epigenetic analyses, without which these analyses cannot be undertaken.

Table 2. Overview sampling and data collection in ORCHESTRA cohorts in COVID-19 patients including long-term sequelae.

| | D0 ¹ | 3 months ¹ ±1 month | 6 months ¹ ±1 month | 12 months ¹ ±1 month | 18 months ¹ ±2 month | Objective |
|---|-----------------|-----------------------------------|-----------------------------------|------------------------------------|------------------------------------|--|
| NP swab | x | x ^{2,3} | x ^{2,3} | x ^{2,3} | x ² | Viral variant and metagenomic sequencing |
| 2 x 2 mL serum tube (serum) | x | x | x | x | x | Immune - serology and type I IFNs autoantibodies |
| 4 mL EDTA blood tube (plasma) | x | x ⁴ | x ⁴ | x ⁴ | x ² | Immune - cytokine and chemokine |
| 1 (if possible 2) 9 mL heparin tube (PBMCs) | x | x ⁴ | x ⁴ | x ⁴ | x ² | Immune - cellular |
| 2 x 2 mL EDTA tube (whole blood) | x | x | x | x | x | Genetic and epigenetic analyses |
| Stool sample (faeces or rectal swab) | x | | x | | x | Metagenomic sequencing |

1. Day 0: first positive SARS-CoV-2 PCR test. Follow-up of 3, 6, 12, and 18 months start from Day 0.
2. Reassessed only if outside the normal ranges at the previous assessment or if clinically indicated.
3. At least one of the three timepoints (month 3, month 6, month 12) is required to perform metagenomic analyses.
4. At least one of the three timepoints (month 3, month 6, month 12) is required.

| | |
|----------|--|
| Level I | Assessments of Level I are mandatory |
| Level II | Customized according to the feasibility of each cohort |

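### The follow-up swab for respiratory metagenomics is marked both conditional and required, and a month-3 swab satisfies the requirement although it cannot fall in the 6-12-month post-recovery window to be analysed

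*Protocol*

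**What the plan says.** Protocol section 3.2, Table 1 has one row for sequencing of nasopharyngeal swabs, covering both viral variants and metagenomics. Baseline is unconditional. Months 3, 6 and 12 carry an asterisk together with footnote 34. Month 18 carries the asterisk only.

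- The asterisk: "Reassessed only if outside the normal ranges at the previous assessment or if clinically indicated".
- Footnote 34: "At least one of three timepoints (month 3, month 6, month 12) is required to perform metagenomics analysis".

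Annex 4, section 3.1.1, Table 2 attaches the same pair to its swab row. Its note 2 is the conditional rule and its note 3 reads "At least one of the three timepoints (month 3, month 6, month 12) is required to perform metagenomic analyses". It also fixes the time origin: "Follow-up of 3, 6, 12, and 18 months start from Day 0", where Day 0 is the first positive test.

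Annex 4 section 2.8 (Task 6.9) describes the use of these swabs. Long-term carriage and the effect of the virus on the respiratory microbiome are to be "assessed on longitudinally collected prospective samples (6-12 months post-recovery and new infections".

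**The concern.** For a recovered patient whose last result was normal, one mark says not to swab and the other says that a swab is needed at some visit. The documents define no normal range for a metagenomic result, so a site cannot apply the asterisk to that analysis as written.

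The requirement is also not tied to the period of interest. Any of three visits meets it, and the earliest lies before the 6-12-month window. If sites use month 3 and then apply the asterisk, the swabs inside the window come from patients with an out-of-range previous result or a clinical indication. Carriage in that group would overstate carriage among recovered patients in general, and the microbiome comparison would describe a selected group. If cohorts resolve the two marks differently, sampling differences would be mixed with cohort differences. A later analysis plan cannot recover swabs that were not taken.

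**Working it through.** The plan states no sample size or power for this analysis, so there is no figure to reproduce. The check is of the schedule itself.

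**1. Is the double mark deliberate?** Compare rows of Table 1 (Annex 4, Table 2 agrees on each):

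- Cytokine and cellular immunity: at least one of months 3, 6 and 12 required (footnote 35), no asterisk at those visits, asterisk only at month 18.
- Stool metagenomics: unconditional at baseline, month 6 and month 18.
- Swab sequencing: asterisk and footnote 34 together at months 3, 6 and 12.

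Of these rows, only the swab row combines the two marks. Table 1 footnote numbers are shifted elsewhere (the adverse-event row also cites 34), but Annex 4 note 3 confirms that footnote 34 belongs to the swab row.

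**2. Does another rule settle it?** Annex 4, Appendix 1 says "The clinical protocol takes precedence over this document". Both documents carry the same pair, so precedence decides nothing. Section 11 adds "Collection, processing and storage of nasopharyngeal samples for SARS-CoV-2 detection and variant identification if clinically relevant", which is again conditional. Its separate screening step accepts a swab or saliva and is not tied to the 6-12-month window.

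**3. Which patterns comply with footnote 34?** Three visits, each swabbed or not, give 2 × 2 × 2 = 8 patterns. Removing the one with no swab leaves 7 that comply. One of these (month 3 only) has no month-6 or month-12 swab; the other 6 have at least one. The patterns are not equally likely, so these counts are not probabilities.

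**4. Which visits can reach 6-12 months post-recovery?** Visits run from Day 0. With recovery r months after Day 0, a visit at month m with tolerance t falls between m − t − r and m + t − r months post-recovery. The documents give no r; 0 to 2 months is assumed.

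| Visit (tolerance) | r = 0 | r = 1 | r = 2 | Touches 6-12? |
|---|---|---|---|---|
| Month 3 (±1) | 2-4 | 1-3 | 0-2 | Never |
| Month 6 (±1) | 5-7 | 4-6 | 3-5 | Only if r ≤ 1 |
| Month 12 (±2, Table 1) | 10-14 | 9-13 | 8-12 | Yes |
| Month 12 (±1, Annex 4) | 11-13 | 10-12 | 9-11 | Yes |
| Month 18 (±3, Table 1) | 15-21 | 14-20 | 13-19 | No |
| Month 18 (±2, Annex 4) | 16-20 | 15-19 | 14-18 | No |

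The month-3 result needs no assumption about r: 4 − r is below 6 for every r ≥ 0.

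**5. Illustration of the selection.** Let s be the share of patients whose required swab is taken at month 3, and q the share of those later swabbed because the asterisk is triggered. The rest (1 − s) are swabbed at month 6 or 12 to meet the requirement. Both s and q are assumed. The share with a month-6 or month-12 swab is s × q + (1 − s).

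- s = 1: q = 0%, 5%, 20% gives 0%, 5%, 20%. Every such swab is a triggered one.
- s = 0.5: the same q gives 50%, 52.5%, 60%. The triggered share is 0%, 0.025/0.525 = 4.8%, and 0.10/0.60 = 16.7%.

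The damage therefore depends mainly on how many sites meet the requirement at month 3, which the protocol leaves open.

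**The case against.** The two marks can be read together. The row holds two analyses and footnote 34 speaks only of metagenomics, so the asterisk may be meant for repeat variant sequencing, which needs virus to be present. Alternatively, the positive Day 0 test may count as the abnormal previous result, so that month 3 is triggered for everyone. Either reading is fair and removes a flat contradiction, but the text states neither. Under both, month 3 still satisfies footnote 34. Under the second, a normal month-3 result can then switch off months 6 and 12.

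Several stronger readings are tempting and are not supported:

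- That the analysis will have no samples. At least one is a minimum, and sites may choose month 6 or 12.
- That only symptomatic patients would be swabbed. The asterisk also covers an out-of-range previous result, which can include a persistent positive without symptoms.
- That a fixed fraction such as one third of patients is lost. This would need an even spread over visits, and nothing in the documents gives one.
- That months 6 and 12 both lie in the window. Visits are counted from Day 0, and month 6 often falls short.

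The scope is also limited. The window appears only in Annex 4. Section 7 names the gut microbiome, and section 12 lists no microbiome endpoint. Annex 4 serves several work packages, so others may supply samples. Whether this row is Level I (mandatory) or Level II (according to feasibility) is not visible in the text available. If it is Level II, the requirement is weaker still. All of this lowers the weight of the point without removing it.

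**Conclusion.** The point holds in a limited form. The swab row carries two marks whose relation is not stated, in both the protocol and Annex 4. On any reading, a month-3 swab meets the requirement while lying outside the window of Task 6.9, so no swab at 6-12 months post-recovery is assured. Swabs that do arise there may be selected on an out-of-range previous result or a clinical indication, which would bias estimates of long-term carriage and microbiome change.

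The size cannot be fixed from the documents: it runs from no loss, if all sites choose a visit in the window, to a cohort with no sample in it. The new-infections part of the task is served by Day 0 swabs and is unaffected. The statements about months 6, 12 and 18 rest on recovery within 0 to 2 months of Day 0; the statement about month 3 rests on no assumption. This is worth correcting for an exploratory task and does not threaten the main aims of the protocol.

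**What to change.** - State in Table 1 and in Annex 4, Table 2 that the asterisk applies to repeat viral-variant sequencing only, not to the metagenomics swab. The diagnostic molecular test has its own asterisked row and stays as it is.
- Reword footnote 34 and Annex 4 note 3 so that the one required follow-up swab is taken, whatever the symptoms or earlier results, at a visit inside the stated window: month 12 by preference, month 6 counting only when it is at least 6 months post-recovery, and month 3 optional. A rule of month 6 or month 12 without that proviso would not secure the window.
- Say how recovery is dated, since the proviso depends on it. Table 1 already records the end of symptoms. Keep swab dates, because a late month-12 visit can pass 12 months post-recovery.
- Flag clinically triggered swabs and analyse them separately.

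The cost is a footnote amendment in both documents, with the ethics review that section 14.1 requires for amendments, and some loss of patients who drop out before the later visit. The required number of follow-up swabs stays at one per patient.
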